## 10 Statistical Analysis

This study intends to examine the safety and performance of the Neqstent used for the treatment for embolization of intracranial aneurysms. The study is not powered to detect statistical significance. As such, clinical judgement is required to assess device safety and performance from the data collected during this study. Clinical judgement will be provided throughout the study by the DSMB.

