### 10.1 Justification of Methodology

This study is designed as a single arm, descriptive study to develop further understanding of the Neqstent. It will provide safety and performance information for subjects from the Neqstent implantation to 24-month follow-up.

At one -month post procedure, the subjects will provide an adverse event profile related to the placement of the device. At six months of the study there will be additional information related to the adverse event profile including any device related instability or deficiency.

Similarly, the subjects will provide a performance profile. At six months post procedure, the information will provide how well the aneurysm has healed or embolized through the analysis of imaging performed by the independent core lab for accuracy and removal of bias. Note: In the

 Cerus Endovascular	Document Number DNQS428-01	Rev. F	Page 44 of 119
Clinical Investigation Plan	Title		
Confidential & Proprietary	Coil Assisted Flow Diversion: A prospective, single arm, multi-center study to assess the safety and performance of Neqstent in adjunctive therapy (CAFI Study)		

event of a Grade 2 or more using the Raymond Roy Scale, a second assessment will be made at 12- month follow-up to re-assess for complete occlusion and will be reported as a secondary efficacy.

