## 10.6 Sample Size Rationale and Statistical Considerations

This is a single arm study designed to provide adequate data for the purpose of a pre-market study. It is expected the 51 patients with evaluable data at 6 month and 12 month follow-up (where necessary) will show adequate evidence of safety and performance of Neqstent device.

For the purpose of sample size calculation, the primary outcome measurement is assumed to be the composite of the listed primary endpoint components.

Extensive literature search was conducted to gather information on the non-inferiority margin. Due to limited results found in literature, the non-inferiority margin for this study,  $\delta = 10\%$ , was chosen to align with the study design.

The sample size estimation was based on the following assumption:

- Success rate of the investigational is expected to be 70%
- Success rate of standard treatment is estimated to be 55%
- Power is set at 80% and one-sided significance level is set at 5%
- Expected rate of attrition is 10%

Based on the assumptions, a total of 46 subjects are required to show that the expected success rate of 70% is different than the true rate of 55% with a delta of 10%. Adding in additional subjects for anticipated loss to follow-up, 51 subjects are needed to be enrolled for a total of 46 subjects with 6 month data.

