### Analysis Population

The safety population consists of all patients who are implanted with the study device. The primary analysis for all safety endpoints will be performed on this population.

The analysis for all primary and secondary study endpoints and baseline, procedural and follow-up characteristics will be performed on an intent-to-treat analysis population which will include all available data for all enrolled subjects. Standard summary statistics will be calculated for all study variables.

 Cerus Endovascular	Document Number DNQS428-01	Rev. F	Page 46 of 119
Clinical Investigation Plan	Title		
Confidential & Proprietary	Coil Assisted Flow Diversion: A prospective, single arm, multi-center study to assess the safety and performance of Neqstent in adjunctive therapy (CAFI Study)		

The primary safety endpoint will be calculated as the proportion of subjects with death of any nonaccidental cause or any major stroke within the first 30 days after treatment or major stroke or death due to neurological cause from day 31 to 6 months after treatment.

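### The 46 subjects said to give 80% power match one arm of a two-arm trial; in this single-arm study the power is about 96% or about 60%, and section 10 says the study is not powered

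*Combined protocol and SAP*

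**What the plan says.** Section 10.6 calls the study single arm and then gives the inputs of a comparative calculation: 70% success expected with the investigational device, 55% with standard treatment, 80% power, one-sided 5% and 10% attrition. On the margin, set at 10%, it says "Extensive literature search was conducted to gather information on the non-inferiority margin". The conclusion is that "a total of 46 subjects are required to show that the expected success rate of 70% is different than the true rate of 55"%; the same sentence names the 10% margin again, as its delta. No formula, software or test is named.

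The rates are attached to an outcome described as follows: "the primary outcome measurement is assumed to be the composite of the listed primary endpoint components".

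On numbers, the section opens with "It is expected the 51 patients with evaluable data at 6 month and 12 month follow-up (where necessary") and closes with "51 subjects are needed to be enrolled for a total of 46 subjects with 6 month data".

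Elsewhere the plan takes a different position. Section 10: "The study is not powered to detect statistical significance". Section 10.1: "This study is designed as a single arm, descriptive study to develop further understanding of the Neqstent". The Analysis Population text in section 10.6 says "Standard summary statistics will be calculated for all study variables", and the Endpoint Analysis text reports the primary performance endpoint as a proportion. Neither contains a hypothesis, null value, success threshold or confidence interval. The synopsis gives a separate, non-statistical reason for 51 subjects: the sponsor's obligation to the notified body.

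**The concern.** A non-inferiority margin and a standard-treatment rate with its own uncertainty belong to a trial with a control group. This study has none, so 46 in total cannot be the answer to that calculation. The null value is also unclear. The margin label points to 55% − 10% = 45%; the wording about differing from a true rate of 55% points to 55%. The two readings need very different sample sizes.

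The power claim also conflicts with the statement that the study is not powered. The composite it refers to has no rule for combining a safety event with an occlusion success, and it is never analysed.

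At stake is whether an ethics committee, regulator or notified body can rely on section 10.6. They are told the study has 80% power for a comparison that it cannot make and does not plan to test. They are not told how precisely a study of this size can estimate the occlusion rate. Section 10.5 provides for re-evaluating the sample size after 10 patients, and this calculation is the only one there is to revisit.

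**Working it through.** **Inputs (all section 10.6).** Investigational rate 0.70; standard rate 0.55; margin 0.10; one-sided 5% (z = 1.645); power 80% (z = 0.842); 46 evaluable, 51 enrolled. (1.645 + 0.842)² = 6.183.

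**1. Reproducing 46.** Two-arm non-inferiority, unpooled variance, per arm:

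n = 6.183 × (0.70×0.30 + 0.55×0.45) / (0.70 − 0.55 + 0.10)² = 6.183 × 0.4575 / 0.0625 = 45.26, rounded up to **46 per arm**, or 92 in total.

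Power with 46 per arm is 80.6%. If 46 were the total of two arms (23 each), power would be 55.1%. Fully pooled variance gives 46.37, hence 47 per arm. Mixed null/alternative variance gives 45.99, hence 46 per arm.

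**2. Single-arm sample size for 80% power.**

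| Method | Null 45% | Null 55% |
|---|---|---|
| Normal, alternative variance: 6.183×0.21/d² | 20.8 | 57.7 |
| Normal, null and alternative variance: (1.645√(p₀(1−p₀)) + 0.842√0.21)²/d² | 23.2 | 64.4 |
| Arcsine | 23.6 | 63.8 |
| Normal, null variance: 6.183×p₀(1−p₀)/d² | 24.5 | 68.0 |
| Exact binomial, first n reaching 80% | 25 | 70 |
| Exact binomial, n from which power stays above 80% | 27 | 73 |

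Here d = 0.70 − p₀, that is 0.25 or 0.15. None of these methods gives 46.

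**3. Single-arm power at n = 46, true rate 70%.** For the exact test, the critical count is the smallest number of successes with type I error at most 5%.

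| | Null 45% | Null 55% |
|---|---|---|
| Critical count | 27 or more | 32 or more |
| Actual type I error | 4.3% | 3.2% |
| Exact power | **96.4%** | **59.7%** |
| Arcsine | 96.6% | 68.0% |
| Normal, null variance | 97.2% | 66.8% |
| Normal, alternative variance | 98.0% | 71.7% |

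If all 51 were evaluable, exact power would be 96.8% and 64.9%.

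**4. Enrolled and evaluable.** 51 × 0.9 = 45.9, so 51 enrolled for about 46 evaluable fits the 10% attrition. The opening phrase, which treats 51 as evaluable, does not.

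**5. What 46 can deliver descriptively.** Near the expected 70%, 32/46 = 69.6%, with Clopper–Pearson 95% CI 54.2% to 82.3%. That is 15.4 points below and 12.7 above, or about ±14 points on average.

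**The case against.** The strongest reply is that little turns on the error. The plan says the study is unpowered and descriptive, only summary statistics are planned, no decision uses the 80%, and the synopsis gives another reason for 51. This stands as a limit on the consequence. It does not rescue the figure: if power is irrelevant, the power claim should not be there, and the synopsis reason is not statistical.

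A second reply is that the margin label makes 45% the natural null, so 46 is more than enough and the error is on the safe side. That is the better-supported reading, and on it the study is over-sized for the stated 80%, not short. But 46 is then not the number required, since 25 to 27 would do by the exact test. The sentence itself also names 55% as the rate to be distinguished from. The 59.7% for that null is the lowest of the four methods; the others run from 66.8% to 71.7%, all still below 80%.

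Third, the two-arm origin is inferred. That is correct, and other variance choices give 46 or 47 per arm. The mismatch with a single arm does not depend on how the sponsor arrived at the number.

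Fourth, the composite and the 51/46 wording are separate from the power error. They are lesser points, and the section's last sentence already settles the second. They sit in the same text and can be corrected in the same edit.

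**Conclusion.** The concern holds. With the plan's own inputs, a true rate of 70% and a one-sided 5% test, 46 evaluable subjects in one arm do not have the stated 80% power on either reading. Exact power is 96.4% against 45% and 59.7% against 55% (60% to 72% across methods). The number 46 fits one arm of a two-arm non-inferiority trial. The claim also contradicts sections 10 and 10.1 and has no counterpart in the planned analysis.

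The result rests on the rates and margin as stated and on reading the null as either 45% or 55%. Only the identification of the two-arm formula is inferred. No primary estimate and no aspect of patient conduct is affected. This should be fixed, because it is the only statistical justification of the sample size.

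**What to change.** **Main fix.**
- Keep 51 enrolled.
- Delete the 80% power statement, the margin and the composite sentence from section 10.6, in line with sections 10 and 10.1.
- Justify the size by the precision of the proportion with Raymond Roy Grade 1 at 6 months, for example 32/46 with exact 95% CI 54.2% to 82.3%.
- Add exact 95% confidence intervals for both primary proportions to the Endpoint Analysis. For safety, a purely illustrative count of 2/51 = 3.9% would have an interval of 0.5% to 13.5%.
- Correct the opening paragraph to 51 enrolled for 46 evaluable.
- Refer the re-evaluation in section 10.5 to this precision basis.

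The cost is text changes only, with no added patients, visits or imaging; the 80% claim is given up. Section 12.2.4 allows simple notification only for non-substantial changes not related to objectives or endpoints, so the sponsor should confirm which route applies.

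**Alternative.** If the sponsor wants a benchmark claim, it must name one performance goal, restate the single-arm power with the method used, add the test to the analysis, and amend section 10. That adds a hypothesis to a descriptive study and would probably need amendment approval. Against 55%, 80% power would need about 70 to 73 evaluable subjects by the exact test.

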Study Size and Duration	
Study Size: The study population will include 51 subjects enrolled and implanted at up to 11 centers.
 
Study Duration: It is expected that the study will take 6 months to enroll a minimum of 51 patients. Follow-ups for the primary endpoint are the 6-month visit and 12-month visit, depending on the Raymond Roy score at the 6-month visit. Total duration of enrollment approximately 6 months, follow-up duration for primary endpoint (6-12 months), 24 months follow-up and reporting (3 months) will take approximately 33 months.
 
Any patient for whom a failed implant attempt is performed will be followed for 1 month, or until resolution of any potential device or implanted related adverse events, whichever occurs last.
 
Any patient who is consented but has no implant attempt will be study exited.

Device Description	
The Neqstent device works by providing a physical barrier between the parent vessel and the intracranial aneurysm neck (as demonstrated by the Neqstent clinical investigations as well as the pre-clinical research) thereby excluding the aneurysm from the parent artery blood flow. The Neqstent implant is sized to provide a proper fit and position across the neck of the aneurysm. Therefore, blood flow is diverted away from entering at the neck, leading to reduction in flow into the aneurysm cavity with subsequent stasis followed by the formation of thrombus within the confines of the aneurysm. As wound healing progresses and fibrosis occurs over the ensuing days and months, it serves to strengthen the physical barrier between the parent vessel and the aneurysm cavity. The weakened vascular tissue of the aneurysm cavity, in particular the dome, is thus protected from the shear wall stresses generated by the previous blood flow.
  
Figure 1 - Neqstent
 
The Neqstent (NQS) (NQS407-XX, NQS409-XX, NQS411-XX) is an intrasacular, self-expanding, embolization device intended for the treatment of intracranial aneurysms. The NQS is shown in Figure 1 and comprises an:
 
Implant
 
The implant is a self-expanding concave shaped device comprised of a double layer nickel-titanium and platinum wire mesh, and a platinum marker. The implant is packaged unconstrained in a protective dispenser hoop with an Introducer preloaded onto the DPW shaft just proximal to the implant.

Clinical Investigation Plan

Title

*Confidential & Proprietary*

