**Table 1. Implant Size Selection Guide**

REF (Catalog Number) – Diameter	Aneurysm Neck (mm)
NQS407-XX – 7 mm	3.0 - 5.0
NQS409-XX – 9 mm	4.0 - 6.0
NQS411-XX – 11 mm	5.0 - 8.0

 Stryker Neurovascular Excelsior® XT-27® (0.027" ID, 2.9F/2.7F OD, 150cm Length)

 Detachable Coil Power Supply: Stryker Neurovascular InZone® Detachment System, REF M00345100940

 Power Supply Detachment Cable: Stryker Neurovascular IZDS Connecting Cable, REF 00345110250

Clinical Investigation Plan

Title

*Confidential & Proprietary*

**Coil Assisted Flow Diversion: A prospective, single arm, multi-center study to assess the safety and performance of Neqstent in adjunctive therapy (CAFI Study)**

Objective and Endpoints	
The primary objective of this study is to document the safety and performance of the Neqstent.
 
1. Primary Safety Endpoint:
 
The proportion of subjects with death of any non-accidental cause or any major disabling stroke within the first 30 days after treatment or major disabling stroke or death due to neurological cause from day 31 to 6 months after treatment.
 
Note: Major Disabling Stroke is defined as an episode of neurological signs or symptoms that persist beyond 24 hours accompanied with evidence of ischemia/infarction on imaging that results in an increase of NIHSS from baseline by <math>\geq 4</math> points and/or an increase from mRS baseline by <math>>2</math>.
 
2. Primary Performance Endpoint:
 
To demonstrate the occlusion rate on the 6 month angiogram as adjudicated by a core laboratory. Success will be defined as complete occlusion demonstrated by a Grade 1 using the Raymond Roy Scale.
 
Note: In the event of a Grade 2 or more using the Raymond Roy Scale, a second assessment will be made at 12 month follow-up to re-assess for remnant stability and/or complete occlusion and will be reported as a secondary efficacy endpoint.

Sample Size	51 subjects will be enrolled to obtain adequate follow-up data for the study to complete sponsor obligation to the notified body.
Number of Sites	Up to 11 sites will enroll in the study.
Study Visits	Baseline, procedure, discharge, one (1) month, six (6) months, twelve (12) months and twenty-four (24) months.

Clinical Investigation Plan

Title

*Confidential & Proprietary*

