
 
Cerus Endovascular
	
Document Number DNQS428-01
	
Rev. F
	
Page 33 of 119

Clinical Investigation Plan
	
Title
		

Confidential & Proprietary
	
Coil Assisted Flow Diversion: A prospective, single arm, multi-center study to assess the safety and performance of Neqstent in adjunctive therapy (CAFI Study)
		

All patients must sign a study-specific consent form prior to the commencement of any protocol-specific assessments and/or procedures. Final qualification will occur during the implant procedure due to the need for confirmation of IA appropriateness with cerebral angiography.

The patient is enrolled at the time of consent and is considered a study subject in the reporting analysis group only when the patient is fully qualified and at least one Neqstent device has been placed into the patient's body. The following listing provides examples of patient enrollment scenarios for the study:

- The patient is not considered enrolled but not included in the primary analysis group in the study: if at the onset of the procedure in the initial DSA, the investigator determined the patient's IA was not suitable for treatment with the device, thus, no attempt was made by the investigator to place the device. The patient will be treated outside of the study per the investigator's usual practices. The reason for not treating the patient must be documented on a study exit form. The patient is not included in the primary analysis group because the Neqstent was never opened or deployed inside the patient. All patients will be listed in the final report.
- The patient is considered enrolled but not included in the primary analysis group in the study: at the onset of the procedure, the investigator determined the subject's IA was suitable for treatment with the device. The investigator attempted but was unable to place the device within the IA and the subject required alternative treatment. The subject is considered enrolled for the purposes of the study but will only be followed through the 1-month visit. All failed implant attempts will be reported in the final report.

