## 11.5 Total Expected Trial Duration

It is expected that the study will take 6 months to enroll a minimum of 51 patients. Follow-ups for the primary endpoint are the 6-month visit and 12-month visit, depending on the Raymond Roy score at the 6-month visit. Total duration of enrollment (6 months), follow-up duration for primary endpoint (6-12 months), 24 months follow-up and reporting (3 months) will take approximately 33 months.

Any patient who is consented but has no implant attempt will be study exited.

All patients must be consented prior to performing study related procedures. All patients that provide consent and are implanted will be followed according to the follow-up schedule. Any patient for whom a failed implant attempt is performed will be followed for 1-month or until resolution of any potential device or implanted related adverse events, whichever occurs last.

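### Section 10.6 gives both 51 and 46 as the number of subjects with evaluable 6-month data, and the plan does not say whether the 51 counts implanted subjects or all enrolled subjects

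*Combined protocol and SAP*

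**What the plan says.** The number 51 appears with several meanings.

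- Section 10.6, opening paragraph: "It is expected the 51 patients with evaluable data at 6 month and 12 month follow-up", with a qualifier that the 12-month part applies only where needed.
- Section 10.6, end of the sizing paragraph: "51 subjects are needed to be enrolled for a total of 46 subjects with 6 month data". The listed assumptions include 10% attrition, and the added subjects are for anticipated loss to follow-up.
- Synopsis, Study Size and Duration: "The study population will include 51 subjects enrolled and implanted at up to 11 centers".
- Synopsis, Sample Size row: "51 subjects will be enrolled to obtain adequate follow-up data for the study".
- Section 11.5, and the synopsis in almost the same words: "It is expected that the study will take 6 months to enroll a minimum of 51 patients".

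Section 7.5 defines enrolment: "The patient is enrolled at the time of consent". It adds that a patient joins the reporting analysis group only once fully qualified and with a device placed. Its scenarios then diverge. A patient found unsuitable on the initial angiogram, with no attempt made, falls under "The patient is not considered enrolled but not included in the primary analysis group in the study". A patient with a failed attempt is counted as enrolled, is left out of the primary analysis group, and is followed through the 1-month visit. Section 11.5 extends that follow-up only until related adverse events resolve. Section 11.3 says that withdrawn subjects are not replaced.

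**The concern.** Two statements in one section give different numbers for the same quantity, the subjects with 6-month data. One of them must be wrong under the plan's own attrition rate.

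The second problem is what counts towards 51. A failed attempt is enrolled under 7.5 but has no scheduled 6-month angiogram, so it cannot contribute to the primary performance endpoint. The 10% allowance is tied to loss to follow-up, and no rate or allowance for failed attempts or late exclusions appears anywhere. A site or sponsor team counting enrolled subjects under 7.5 and one counting implanted subjects under the synopsis would stop recruitment at different points.

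The evaluable number sets the precision of the occlusion rate. The word enrolled also affects the denominator, because the Analysis Population text in 10.6 defines the intent-to-treat set as all enrolled subjects.

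**Working it through.** **Inputs.** From 10.6: 46 subjects with 6-month data, 51 enrolled, 10% attrition, 70% expected success. The documents give no rate of non-implantation for this device, so f, the share of the 51 who are counted but never successfully implanted, is assumed.

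**Step 1: reproduce the plan's inflation.** 46 / 0.9 = 51.1, which is 51 to the nearest whole number (52 if rounded up). Also 46 x 1.1 = 50.6, or 51. In reverse, 51 x 0.9 = 45.9. So 51 enrolled to give 46 reproduces, apart from rounding.

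**Step 2: test the opening sentence of 10.6.** If 51 were the evaluable number, the study would need 51 / 0.9 = 56.7, so 57 subjects. No section plans for 57. The figure of 51 evaluable does not fit the rest of 10.6.

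**Step 3: how much loss 51 can absorb.** 51 - 46 = 5 subjects, and 5 / 51 = 9.8%. The 10% attrition assumption uses all of it, leaving nothing for failed attempts or late exclusions.

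**Step 4: what follows if non-implanted patients count towards 51.** Expected number with 6-month data = 51 x (1 - f) x 0.9. Count needed to expect 46 = 46 / (0.9 x (1 - f)), rounded up. The chance of at least 46 is from a binomial with 51 trials and probability 0.9 x (1 - f).

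| f (assumed) | Expected with 6-month data | Chance of at least 46 | Count needed to expect 46 |
|---|---|---|---|
| 0% | 45.9 | 60% | 52 |
| 2% | 45.0 | 43% | 53 |
| 5% | 43.6 | 23% | 54 |
| 10% | 41.3 | 6% | 57 |

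The row f = 0% is the synopsis reading, in which all 51 are implanted. Even there the chance is 60%, because the target sits at the expected value; that is ordinary for attrition inflation.

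**Step 5: effect on precision.** The approximate 95% half-width at 70% success is 1.96 x sqrt(0.7 x 0.3 / n). It is 13.2 percentage points at n = 46, 13.7 at n = 43 and 14.0 at n = 41.

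**The case against.** A reader might infer that the plan sets 51 as a count of consented patients and so will fail to deliver 46. The documents do not support that.

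- Nowhere is 51 called a number of consents. That reading comes from joining the word enrolled in 10.6 to the definition in 7.5, and 7.5 contradicts its own definition for patients with no attempt.
- The most explicit description, in the synopsis, is of implanted subjects, and on that reading 51 does give 46 to rounding.
- Failure is not certain on any of the assumed rates: 46 is reached if five or fewer are lost in total, a 43% chance at f = 2% and 23% at 5%.
- Section 11.5 and the synopsis call 51 a minimum, and 10.5 says that the sample size will be re-evaluated after 10 patients.
- The only implant rate in the documents, 93%, comes from a retrospective series of another device that included ruptured aneurysms. It does not estimate f here, where images go to a selection committee before the procedure is scheduled and the first implants at a new centre are proctored.

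All of this stands, as does the point that section 10 calls the study descriptive and not powered for significance, so that a few evaluable subjects either way matter little.

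Two things are left. The conflict between 51 and 46 evaluable in 10.6 needs no assumption. And failed attempts are enrolled under 7.5 whichever way its other conflict is settled, yet yield no scheduled 6-month image.

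**Conclusion.** The concern holds in a limited form. The figure of 51 patients with evaluable data in 10.6 is wrong by the plan's own arithmetic; the consistent figure is 46 (45.9 before rounding). The target of 51 has no single definition. If patients without a successful implant count towards it, 46 is not the expected yield; the expected number is 45.0, 43.6 or 41.3 at an assumed 2%, 5% or 10% not implanted, with 10% attrition among the rest. These rates only illustrate the direction and scale, and should not be written into the protocol as a forecast. If the 51 are implanted subjects, there is no shortfall beyond rounding.

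The consequence is small: less than one percentage point of half-width between 46 and 41 subjects. This is a correction worth making, not a threat to the study.

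**What to change.** In 10.6, change the number of patients with evaluable data in the opening paragraph from 51 to 46. State in the sizing paragraph that the target of 51 counts implanted subjects, as the synopsis already does, and that failed attempts and consented patients with no attempt do not count towards it.

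Use the same term in the Sample Size row of the synopsis, in 7.5 and in 11.5. In 7.5 (and the matching synopsis text), settle whether a consented patient with no attempt is enrolled.

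The cost is a wording amendment and possibly a few more consents. To implant 51 at an assumed 2%, 5% or 10% not implanted would take 51 / 0.98, 51 / 0.95 or 51 / 0.90 consents, rounded up to 53, 54 or 57.
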